The decision on dose escalation/de-escalation/stopping or continuation for the patient cohort will be taken by the Study Management Group based on data review of each dose group considering safety, efficacy, drug concentration, and in conjunction with the prespecified criteria.					
End of Cohort 1 SMG meeting held on March 23, 2023 recommended to proceed to cohort 3 if patients in cohort 2 shows insufficient anticoagulation effect. Insufficient anticoagulation effect is defined when 3 patients or more treated within cohort 2 dosing regimen experienced at least one ACT < 200 seconds and confirmed by Ad Hoc SMG meeting.					
All patients will be administered a loading dose of aspirin approximately 325 mg (not exceeding 400 mg, if not already on maintenance ASA dose) and will stay on 75-100 mg/day					

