6 INVESTIGATIONAL PLAN

6.1 Description of Overall Study Design and Plan

This is an open-label, sequential-dose escalation/de-escalation trial testing 3 dose levels of MT1002 in patients undergoing PCI due to ACS with NSTEMI. Three doses of MT1002 will be sequentially tested in cohorts of 6 patients each to achieve target ACT.

Pre-specified dose escalation/de-escalation/stopping/continuation rules for the patient cohorts are shown in Table 1 below.

Table 1 Rules for Dose Escalation/De-Escalation/Stopping/Continuation

Continue to next higher dose group if:	Stop study drug infusion temporarily in an individual patient if:	Stop dose group and de-escalate according to protocol if:	Continue the same dose in the next patient cohort (to get more data for initial dose) if:	Stop the study if:
$\leq 2/6$ pat peak ACT > 300	Any ACT > 350 or < 180	$\geq 3/6$ pat peak ACT > 300	$\leq 3/6$ pat peak ACT > 300	> 3/6 pat peak ACT > 350
≥ 3 pts. peak ACT < 200 (Cohort 2)				AND
$\leq 1/6$ pat with BARC 3 to 5	BARC 3 to 5	$\geq 2/6$ pat with BARC 3 to 5	$\leq 1/6$ pat with BARC 3 to 5	> 2/6 pat with BARC 3 to 5
				OR
No SAE due to study drug	Any AE/SAE due to study drug that requires switching patient to standard of care	$\geq 2/6$ SAEs due to study drug	No SAE due to study drug	$\geq 2/6$ SAEs due to study drug

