In $\leq 1/6$ pat lab values preventing dose escalation such as LFT up by $\geq 2 \times$ from baseline; platelet count < 50,000; QTcF interval > 500 ms or > 60 ms change from baseline, based on ECGs; or study drug related vital sign changes that require stabilization of hemodynamics with positive inotropes	Lab values preventing dose continuation such as LFT up by $\geq 2 \times$ from baseline; platelet count < 50,000; QTcF interval > 500 ms or > 60 ms change from baseline, based on ECGs; or study drug related vital sign changes that require stabilization of hemodynamics with positive inotropes	In $\geq 2/6$ pat lab value preventing dose escalation such as LFT up by $\geq 2 \times$ from baseline; platelet count < 50,000; QTcF interval > 500 ms or > 60 ms change from baseline, based on ECGs; or study drug related vital sign changes that require stabilization of hemodynamics with positive inotropes	In $\leq 1/6$ pat lab values preventing dose escalation such as LFT up by $\geq 2 \times$ from baseline; platelet count < 50,000; QTcF interval > 500 ms or > 60 ms change from baseline, based on ECGs; or study drug related vital sign changes that require stabilization of hemodynamics with positive inotropes	In $\geq 3/6$ pat lab values preventing dose escalation such as LFT up by $\geq 2 \times$ from baseline; platelet count < 50,000; QTcF interval > 500 ms or > 60 ms change from baseline, based on ECGs; or study drug related vital sign changes that require stabilization of hemodynamics with positive inotropes

Abbreviations: AE, adverse event; ACT, activated clotting time; BARC, Bleeding Academic Research Consortium; ECG, electrocardiogram; LFT, liver function test; pat, patient; QTcF, QT interval corrected by Fridericia's formula; SAE, serious AE.

The decision on dose escalation/de-escalation/stopping or continuation for the patient cohort will be taken by the Study Management Group based on data review of each dose group considering safety, efficacy, drug concentration, and in conjunction with the prespecified criteria.

End of Cohort 1 SMG meeting held on March 23, 2023 recommended to proceed to cohort 3 if patients in cohort 2 shows insufficient anticoagulation effect. Insufficient anticoagulation effect is defined when 3 patients or more treated within cohort 2 dosing regimen experienced at least one ACT<200 seconds and confirmed by Ad Hoc SMG meeting.

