8.5 Prior and Concomitant Therapy

8.5.1 Prior and Concomitant Medications

Restricted prior therapies that exclude patients from the study are provided in Section 7.2.

All cardiovascular, antiplatelet, anticoagulant, and diabetic medications and other treatments taken by the patient during the study, including those treatments initiated or ongoing within 48 hours before the start of the study, must be recorded on the eCRF (based on patient/caregiver report and/or medical records).

Concomitant anticoagulant medications before enrollment:

Unfractionated heparin: UFH administered to patients before enrollment will be discontinued at the time of enrollment with MT1002 allocation (if not already discontinued). MT1002 can be administered after discontinuation of intravenous UFH or 4 hours after subcutaneous UFH discontinuation provided ACT is <200 seconds. The wash-out period for UFH should help to

ensure complete UFH elimination⁵ to avoid initial ACT increase due to residual heparin effect that could confound the analysis of MT1002's effect on the indices of coagulation.

Low molecular weight heparin: LMWH administered to patients before enrollment will be discontinued at the time of enrollment with MT1002 allocation (if not already discontinued). MT1002 can be administered 8 hours after subcutaneous low molecular weight heparin discontinuation provided ACT is <200 seconds.

Patients receiving fondaparinux for the index admission before enrollment with MT1002 allocation should not be included in the study.

Background therapy:

Acetylsalicylic acid: On admission, all patients will be administered a loading dose of aspirin approximately 325 mg (not exceeding 400 mg, if not already on a maintenance dose) and will stay on 75-100 mg/day (according to local countries clinical practice guidance) as maintenance therapy. Patients should continue aspirin for the remainder of the study period (i.e., through 30 days post-dose) or longer per local standard of care. This background medication will not be provided as part of the clinical trial supplies, unless required by local laws and regulations.

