- ⁱ MT1002 will be initiated as close to the start of PCI as possible. MT1002 should be initiated during diagnostics angiography when indication for PCI is confirmed, provided the early PCI is indicated right after the coronary angiography. PCI can start after MT1002 initiation as soon as ACT is confirmed to be ≥ 200 sec or within 30 min after start of MT1002, whichever occurs first.
- ^j Pharmacokinetic samples will be taken at Day 1 pre-dose; at 5 (± 1) min after MT1002 intravenous injection; and 0.5 (± 5 min), 4 (-5 to 10 mins, 5-10 min before the infusion completion), 6 (± 15 min), 8 (± 15 min), and 24 (± 15 min) hours post-dose initiation.

- ^k ACT, aPTT, and PT, TT, FIB, INR will be taken at Screening; on Day 1 pre-dose; at 5 (± 1) min after MT1002 intravenous injection; and 0.5 (± 5 min), 4 (-5 to 10 mins, 5-10 min before the infusion completion), 6 (± 5 min), 8 (± 15 min), and 24 (± 15 min) hours post-dose initiation.
- l Between screening and Pre-PCI within 48 hours, Vital signs, 12-lead ECG, CK-MB, cardiac troponin I (troponin T can be measured if the local site does not have the troponin I test), ACT, aPTT, PT, TT, FIB, INR, PA (PFA100 or PFA 200), Hematocrit, hemoglobin, platelet count, RBC and WBC counts take once; screening and Pre-PCI beyond 48 hours, should take twice before PCI.

Table 5 Time Points for Platelet Aggregation, Cardiac Biomarkers, Coagulogram, and Pharmacokinetics

Time points/ blood tests	Screening	Day1 pre-dose	5 min (± 1 min) post-dose initiation	0.5 h (± 5 min) post-dose initiation	4h (-5 to 10 min) post-dose initiation, 5-10 min before the infusion completion)	6h (± 15 min) post-dose initiation	8 h (± 15 min) post-dose initiation	24 h (± 15 min) post-dose initiation
PA	X		X	X	X	X	X	X
Cardiac biomarkers ^a	X	X		X	X	X	X	X
ACT, aPTT, PT, TT, FIB, INR	X	X	X	X	X	X	X	X
PK		X	X	X	X	X	X	X

Abbreviations: ACT, activated clotting time; aPTT, activated partial thromboplastin time; h, hours; PA, platelet aggregation; min, minutes; PK, pharmacokinetics; PT, prothrombin time; TT, Thrombin time; FIB, Fibrinogen; INR, International Normalized Ratio.

^a Creatine kinase-MB, cardiac troponin I (troponin T can be measured if the local site does not have the troponin I test).

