9.2.2 Pre-percutaneous Coronary Intervention Day 1 (Baseline)

Enrollment should occur as close to the planned start of PCI as possible, and MT1002 dosing should be started as close to the actual start of PCI as possible. MT1002 should be initiated during diagnostics angiography when indication for PCI is confirmed, provided the early PCI is indicated right after the coronary angiography. Study drug should be administered in the catheterization lab.

Either radial access/distal radial access PCI or femoral access PCI will be used in this study. It is up to the discretion of the Principal Investigator what type of stent(s) will be used.

- Confirm that diagnostic catheterization indicates the need for PCI. The Investigator's interpretation of the diagnostic angiogram, TIMI flow grade, the treatment plan, and if the patient remains eligible to continue the study should be recorded.
- Record vital signs (body temperature, respiration rate, heart rate, and systolic and diastolic blood pressure).
- Perform a 12-lead ECG.
- Confirm all screening procedures have been completed and that the patient meets all other eligibility requirements and record patient enrollment with identification of allocated study drug vial.
- Record all changes in concomitant medications including cardiovascular, antiplatelet, anticoagulant and diabetic medications administered since screening.
- Obtain pre-dose baseline central cardiac biomarkers (troponin I [troponin T can be measured if the local site does not have the troponin I test], and CK-MB) immediately before PCI; and hemoglobin, hematocrit, platelet count, and RBC and WBC counts; coagulogram (ACT, aPTT, PT, TT, FIB, INR according to the time points in the Schedule of Assessments [Table 4] and Table 5), Pharmacokinetic blood sampling (according to the time points in the Schedule of Assessments [Table 4] and Table 5).

Additional ACT test can be performed if MT 1002 dose is adjusted. The ACT test value and time of test will be recorded in eCRF. These blood samples may be obtained either peripherally or through the arterial sheath.

- Collect PK plasma samples according to the time points in the Schedule of Assessments (Table 4) and Table 5.
- Perform a PA (by PFA100 or PFA200) according to the time points in the Schedule of Assessments (Table 4) and Table 5.

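### The rule for moving from Cohort 2 (0.60 mg/kg) to Cohort 3 (0.75 mg/kg) is stated two non-equivalent ways: peak ACT below 200 sec in Table 1, at least one ACT below 200 sec in the text.

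*Combined protocol and SAP*

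**What the plan says.** The current protocol gives the Cohort 2 criterion in four places, in two forms.

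- **Peak form.** Table 1 in Section 6.1, in the column for continuing to the next higher dose group, counts three or more "pts. peak ACT < 200 (Cohort 2"). The rules table in the synopsis has the same entry.
- **At-least-one form.** The text after Table 1 records the SMG meeting of 23 March 2023 and defines insufficient effect as the case where "3 patients or more treated within cohort 2 dosing regimen experienced at least one ACT<200 seconds and confirmed by Ad Hoc SMG meeting". The synopsis repeats it: "experienced at least one ACT < 200 seconds and confirmed by Ad Hoc SMG meeting".

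The SMG takes the decision "considering safety, efficacy, drug concentration, and in conjunction with the prespecified criteria".

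Neither form lists the readings that count. Table 4, footnote k, schedules ACT widely ("TT, FIB, INR will be taken at Screening; on Day 1 pre-dose; at 5" minutes, then 0.5, 4, 6, 8 and 24 hours). Section 9.2.2 adds: "Additional ACT test can be performed if MT 1002 dose is adjusted". The 30-minute window in Sections 6.1 and 8.2 belongs to the rescue rule and the treatment goal, not to this criterion.

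**The concern.** A peak below 200 sec means that every counted reading is below 200 sec. At least one reading below 200 sec needs a single low value. Take a patient at 190 sec at 5 minutes and 215 sec at 30 minutes. This patient meets the ACT goal in Section 8.2, is not rescued under Section 6.1, and does not count under Table 1. Under the text, the same patient counts towards finding 0.60 mg/kg insufficient.

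The rule feeds the judgement on 0.60 mg/kg and the opening of a further cohort of 6–8 patients. The data are open-label, so two available wordings leave room to choose between them after the readings are known.

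**Working it through.** The plan gives no operating figure for this rule, so there is none to reproduce. The check asks how far apart the two forms can be.

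**Direction.** On the same set of readings, any patient whose peak is below 200 sec also has at least one reading below 200 sec. The table event is nested in the text event, so P(disagree) = P(text fires) − P(table fires), and only the text can fire alone.

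**Inputs.** Table 3, 0.60 mg/kg row: 194.5±28.6 sec at 5 min and 216.2±15.7 sec at 30 min.

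Assumptions: normal values; ± read as SD; independent patients; n = 6 as in Table 3 (the synopsis dose table allows 3–6); only the 5- and 30-minute readings counted; correlation ρ between them from 0 to 1. Counting further readings could only make the text easier to meet and the table harder.

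**Volunteer values.**

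- P(5 min <200) = Φ((200 − 194.5)/28.6) = 0.576
- P(30 min <200) = Φ((200 − 216.2)/15.7) = 0.151

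| | ρ = 0 | ρ = 1 |
|---|---|---|
| Both <200 (table), per patient | 0.576 × 0.151 = 0.087 | 0.151 |
| Either <200 (text), per patient | 0.576 + 0.151 − 0.087 = 0.640 | 0.576 |
| Table: P(≥3 of 6) | 0.011 | 0.048 |
| Text: P(≥3 of 6) | 0.872 | 0.786 |
| Disagree | 0.861 | 0.738 |

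**What Cohort 1 says about those values.** The Version 6.0 entry reports that at 0.90 mg/kg, 3 of 6 patients exceeded 300 sec at 5 min and 1 of 6 at 30 min. Table 3 expected 209.7±19.2 and 212.3±29.5.

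- 5 min: 3/6 above 300 puts the mean near 300; shift 300 − 209.7 = +90.3 sec.
- 30 min: 1/6 above 300 puts the mean at 300 − 0.967 × 29.5 = 271.5; shift 271.5 − 212.3 = +59.2 sec.
- Exact 95% limits for 3/6 are 11.8–88.2%, a 5-min shift of +68 to +113 sec. For 1/6 they are 0.4–64.1%, a 30-min shift of +10 to +98 sec.

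**P(disagree) at 0.60 mg/kg under such shifts.**

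| Assumed change from volunteer values | P(disagree) |
|---|---|
| +10 sec at both times | 53–59% |
| +20 sec | 27–28% |
| +30 sec | 9% |
| +40 sec | 2% |
| +50 sec | 0.4% |
| Cohort 1 estimates (+90.3, +59.2) | <0.001% |
| Means and SDs × 300/209.7 = 1.43 | 0.04% |
| Lower 95% limits (+68, +10) | 0.2–0.4% |
| +90 at both times, SDs doubled | 0.6% |
| +45 at both times, SDs doubled | 16–19% |

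In the last row, +45 is the lower 5-min limit when the 0.90 mg/kg SD is doubled to 38.4.

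**The case against.** The text may simply be the definition. It says so, gives the SMG meeting it came from and includes a confirmation step, while the table entry is a short cell. The Version 6.0 entry also uses the word peak for single timed readings, so the cell may be shorthand. This is a fair guess at intent and supports keeping the text version. It does not remove the conflict: Table 1 itself sets any ACT (individual-patient column) apart from peak ACT (cohort columns), and no section says which form governs.

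The SMG must also confirm the move and weighs other data, so P(disagree) is not the probability of a different decision. That stands. But the SMG works alongside the prespecified criteria, and here those criteria differ.

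The definition may be completed elsewhere. Section 14.8 announces an SMG charter and Section 14 a SAP that supersedes the protocol where they differ. Neither was available, so this cannot be ruled out.

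Two stronger readings are tempting:

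- **The text counts pre-dose samples.** A reader might infer that heparin-treated patients meet the rule before any MT1002 is given, since Section 8.5.1 allows dosing "4 hours after subcutaneous UFH discontinuation provided ACT is <200 seconds", with a like condition for low molecular weight heparin. The text concerns an anticoagulation effect in patients treated within the cohort's regimen, and a pre-dose sample cannot show one. The documents also give no heparin share, so no probability can be attached.
- **The rules will usually disagree.** The 74–86% figure invites this, but it rests on volunteer values that Cohort 1 contradicts.

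**Conclusion.** The inconsistency is certain: one dose-decision threshold has two non-equivalent statements, each appearing twice, and no stated precedence. Its practical size is unknown. The chance of disagreement is 74–86% if patients behave like the Phase 1 volunteers and well under 1% at the shifts Cohort 1 suggests. Six patients do not settle the matter: a lower-limit shift with doubled SDs still gives 16–19%, though the documents offer no source for doubling the SDs. Carrying a shift seen at 0.90 mg/kg over to 0.60 mg/kg is a further assumption.

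The safety consequence is small. A premature trigger opens a starting regimen of 0.75 mg/kg + 1.6 mg/kg/h. That is below the 0.90 mg/kg + 1.8 mg/kg/h given to six Cohort 1 patients without serious adverse events, major bleeding or major adverse cardiovascular events (Version 6.0 entry). The 30-minute rescue rule still applies. All endpoints are summarised descriptively, so no test or error rate is affected. What is at stake is a clear, prespecified basis for calling 0.60 mg/kg insufficient. This should be fixed; it is not a safety alarm.

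**What to change.** Before Cohort 2 data are reviewed, put one wording in Table 1, the Section 6.1 text and their two synopsis copies.

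- Keep the SMG's definition from the text.
- In Table 1 and its synopsis copy, replace the peak criterion with at least one ACT below 200 sec in 3 or more Cohort 2 patients.
- In all four places, limit the count to readings taken during the MT1002 infusion and before any switch to rescue: the scheduled 5-minute and 30-minute readings. State whether the 4-hour and unscheduled readings count.

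If the SMG did intend the peak, align the text to the table instead. The choice should be made knowingly: on volunteer values the text form fires 79–87% of the time and the table form 1–5%. Check the SMG charter and the SAP for the same wording.

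The cost is amendment wording in four places. No extra data or patients are needed.
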